#### **(d) Sampling**

**Sample size determination:** Sample sizes for our qualitative research activities (IDIs, DIs, and FGDs) are consistent with guidance to reach saturation and previous experience. Our study is not powered to detect statistically significant intervention effects on our behavioral outcomes. Rather, our focus is to assess the intervention's acceptability, usability, and whether it produces clinically meaningful improvements on our primary outcomes. Positive findings, even if not statistically significant, will provide preliminary evidence in support of conducting a larger pilot trial of this novel intervention. Nonetheless, based on enrolling 30 subjects, 80% power, and 10% two-sided type I error rate (Bonferroni corrected), the minimum detectable effect size in a pre-post comparison (paired t-test) of each subject's scores on our primary outcomes of 1) anticipated HIV stigma from family members, 2) internalized pregnancy stigma, 3) HIV disclosure self-efficacy, and 4) pregnancy disclosure self-efficacy is a Cohen's dz (standardized difference scores) of .59. This is considered a "medium" effect size. As a secondary outcome, we will assess safe disclosure behaviors to determine whether we can obtain valid and reliable measures of the incidence and timing of disclosure since this would be a primary outcome in a scaled-up trial of the intervention. Our proposed sample size and single pre-post intervention group design is appropriate for this pilot study's purpose of assessing time-related patterns and consistent with guidelines for assessing clinically meaningful improvements in outcomes.

**Sampling procedure:** We will use purposive sampling techniques to select ALHIV and caregivers from our urban and rural study settings based on inclusion criteria. Recruitment of pregnant ALHIV

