**(Components 1, 2, and 3):** For individual in-depth interviews (IDIs) and focus group discussions (FGDs), we will select adolescents who have disclosed and not disclosed their pregnancy and/or HIV status to a caregiver. For dyadic interviews (DIs), we will purposively select adolescents who have disclosed both conditions to their caregiver. Pilot study participants will not have disclosed at least one of the two conditions to a caregiver. In both our urban and rural sites, we will recruit participants from maternal and child health (MCH) clinics in public health facilities. Kisumu and Siaya County Directors of Health will assist us to identify public health facilities serving large numbers of pregnant ALHIV. As in our previous research, we will visit the facilities to seek assistance from MCH providers in referring potential participants to our study staff. To protect their privacy, MCH staff will inform potential participants (i.e., pregnant unmarried ALHIV aged 15-19) about our study and ask if they are interested in participating.

MCH providers will give interested individuals the following options: (1) give verbal consent to the MCH provider to allow their contact information to be shared securely with study staff, (2) be given contact information of the study staff so that the adolescent can call at her convenience, and/or (3) give verbal consent for the MCH provider to call study staff in their presence to schedule a meeting. Providers assisting with recruitment will be trained in human subjects protections and given a script to use when informing potential participants about the study. We will adjust our recruitment procedures based on any new clinic/hospital protocols that have been implemented to mitigate the spread of COVID-19. Providers will receive financial support to assist with recruitment (e.g., for cell phone airtime and transport).

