We will also use snowball sampling techniques to recruit participants. We will ask ALHIV and caregivers who participate in study activities if they are willing to assist with recruitment. To ensure the privacy of potential participants, we will provide participants who are willing to assist with recruitment with up to two flyers each to pass on to potentially eligible ALHIV and caregivers in their communities. The flyer will include instructions for individuals who are interested in participating in the study. We may also advertise the study to pregnant ALHIV by placing posters with a brief study description and contact information in health facilities and other public venues that interested pregnant ALHIV may use to contact research staff. We used this procedure in our previous study.

Our staff will be trained on COVID-19 protective measures (i.e., wearing masks, washing hands, and keeping a safe distance) and on how to explain these measures to potential participants using culturally appropriate terms. They will be provided with surgical masks and hand sanitizer for themselves and to offer to participants they interact with. Staff will meet participants at a location that is comfortable, convenient, and private for the potential participants. The staff will use a script to provide potential participants with information about the study, answer questions, and use a screening questionnaire to confirm eligibility for the research activity. They will enroll eligible participants while meeting our purposive sampling goals of (1) having equal numbers of participants from the rural (Siaya) and urban (Kisumu) counties, and (2) having the HIV and pregnancy disclosure experience appropriate to the research activity. For the DIs, we will not recruit ALHIV who decline to identify a caregiver to invite for the DI. Participants will participate in one study activity. Regular meetings during the recruitment period will be held by research staff and clinicians assisting with recruitment to identify and overcome difficulties during this phase. These strategies worked well for the team in a previous study.

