**FGDs with adolescents (Aim 1 Phase 2, Component 2) and caregivers (Aim 2, Component 4):** For Aim 1 there will be 4 FGDs (8 participants each) conducted with pregnant ALHIV (2 rural and 2 urban). For Aim 2, there will be 4 FGDs (8 participants each) conducted with caregiving family members (2 rural and 2 urban) in Round 1 and 4 FGDs in Round 2 (2 rural, 2 urban). FGD sessions will be facilitated by a trained KEMRI moderator fluent in the local languages who will use a semi-structured guide. Each session will last up to two hours. The adolescents will be asked for feedback on the content and flow of the intervention module and their opinion on the mock-ups (e.g., appropriateness, realism, appeal, and plans for using text messaging). Caregivers in Round 1 will be asked about our plans for developing a digital intervention for ALHIV and approaches for involving family caregivers. Caregivers in Round 2 will be asked for feedback about the final Aim 1 intervention prototype and views on a potential complementary digital intervention for caregivers. All FGDs will be conducted in a location providing privacy and confidentiality.

Using Aim 1 findings, the research team will develop an intervention prototype. As part of this process, PIRE and KEMRI staff will test versions in order to finalize the prototype.

**Pilot study with adolescents (Aim 1, Component 3):** The pregnant ALHIV participants will complete a 40-50-minutes baseline survey that includes questions about demographics, HIV and pregnancy stigmas, and disclosure. All participants will receive a one-on-one intervention session in which they will be provided with a study mobile phone with internet access, guided on how to access the prototype intervention, and instructed to go through the intervention. Research staff will take notes of observations made while participants are using the app. Immediately after participating in the intervention, the adolescents will complete a questionnaire asking about the intervention's acceptability and usability. Intervention sessions may last up to two hours. Altogether, the baseline data collection and intervention session will last approximately 3 hours. Participants will take a follow-up survey two weeks after the intervention session, which will last about 40-50 minutes.

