## **11. DATA MANAGEMENT:**

**Data Collection and Management:** Data sources will include electronic data files, audio-recordings, transcripts, and field notes obtained from research activities which will include interviews, focus groups, and surveys. Research team members will audio-record the interviews and focus groups and take notes. All audio recordings will be transcribed and translated. The research team will develop and use codebooks for each qualitative research activity to analyze the data. For the pilot study, the research team will analyze the pre- and post-treatment questionnaire data to assess if the intervention produced clinically meaningful improvements on outcomes of interest. Participants will complete a survey at baseline, immediate post-intervention, and two-week follow-up. We will use an adaptation of the user version Mobile Application Rating Scale (uMARS), modified for our study, to assess the intervention's acceptability and usability. Other measures, based on our conceptual framework (Fig. 1), will include demographics, stigma (HIV: anticipated from family members, internalized, coping; pregnancy: internalized), disclosure self-efficacy, and disclosure to family members. Survey data will be collected using computer-assisted interviewing (CAI) techniques on secure password-protected devices. All study data will be transferred from data collection devices to KEMRI's secure servers daily. Data will be transferred from KEMRI to PIRE as encrypted data files. At PIRE, the data will be stored on secure servers. Only research staff authorized by the PI ([name]) and Co-PI ([name]) will have access to the data. PIRE staff will conduct further data cleaning, coding, and data analysis.

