Study monitoring and oversight: The PI will obtain approval for the study from the PIRE and KEMRI IRBs. Research staff will receive training in protection of human subjects, research protocols, use of the study's Data Safety and Monitoring Plan (DSMP), and maintaining participant confidentiality. Input will be obtained from the Kenyan team to ensure our plans for monitoring participant safety are appropriate to the local situation, and staff will be trained on the procedures. The PI, co-investigators, and study staff are experienced in conducting research in sub-Saharan Africa, including in the Nyanza region in Kenya and in data collection with HIV-infected adolescents, pregnant adolescents, and family member caregivers. The PI is experienced in monitoring participant safety of HIV-infected, pregnant, and emotionally distressed youth and overseeing field work in Kenya. The study will receive review and oversight from the IRBs. Details of our DSMP are provided in an attachment.

Benefits: Participants may experience personal satisfaction from communicating with researchers about topics relevant to pregnant ALHIV such as stigma, disclosure and family support; being treated as knowledgeable stakeholders; and being part of a study that could potentially help people in similar circumstances of need. The adolescents who participate in the pilot study may benefit from receiving the digital intervention session which will be designed to help adolescents like them improve stigma knowledge and coping skills, HIV and pregnancy disclosure skills, and enlisting support of caregiving family members. The study's risks are reasonable in relation to the potential benefits to participants and others.

(b) **Animal Subjects.** Not applicable.

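### Does admitting girls who have already disclosed one condition undermine the pilot's disclosure outcomes?

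*Combined protocol and SAP*

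**What the plan says.** Section 10(d), on recruitment of pregnant adolescents, gives the pilot's disclosure criterion: "Pilot study participants will not have disclosed at least one of the two conditions to a caregiver". One condition may therefore already be known to a caregiver, but not both. Staff will "use a screening questionnaire to confirm eligibility for the research activity".

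The sample size paragraph of the same section names four primary outcomes and bases a paired pre-post calculation on 30 subjects. It ends: "3) HIV disclosure self-efficacy, and 4) pregnancy disclosure self-efficacy is a Cohen's dz (standardized difference scores) of .59". It adds that "Positive findings, even if not statistically significant, will provide preliminary evidence in support of conducting a larger pilot trial of this novel intervention". As a secondary matter, the pilot is to find out whether it can obtain "valid and reliable measures of the incidence and timing of disclosure since this would be a primary outcome in a scaled-up trial".

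Section 10(e) describes a "baseline survey that includes questions about demographics, HIV and pregnancy stigmas, and disclosure". Section 11 lists among its measures disclosure self-efficacy "and disclosure to family members". Section 13 plans frequencies, measures of central tendency and a descriptive analysis of two time points. Section 8 says that no formal hypothesis will be tested.

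No section sets a quota for disclosure status in the pilot, splits an outcome by it, or says who counts as at risk of a new disclosure.

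**The concern.** For each condition, the pilot can mix girls who still have to tell a caregiver with girls who have done so. A girl who has already told her caregiver that she is pregnant may begin with high confidence on that score and have little room to gain. If so, the mean over everyone understates the gain among girls with that conversation still ahead. With no test planned, the observed change is part of what will support a larger study, and a reader could not separate the effect of the intervention from the mix of girls enrolled.

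Disclosure incidence raises a similar question. If the event is a first disclosure to a caregiver, a girl who has already made it cannot have the event, and a rate over all 30 is capped below 100%. Because the pilot is meant to show whether incidence can be measured validly, a missing denominator looks like a gap in the very thing being tried out.

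**Working it through.** **1. The plan's own figure.** Inputs from section 10(d): n = 30, power 80%, two-sided type I error 10% with Bonferroni correction, four primary outcomes. Dividing by four is my reading: 0.10/4 = 0.025 per outcome. For a paired t-test, power is approximately 1 − F(t(1−α/2, n−1)), where F is the noncentral t distribution with n − 1 degrees of freedom and noncentrality dz·√n. Solving for 80% power gives dz = 0.589, which is the stated .59. The figure is right when all 30 girls contribute to each outcome.

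**2. Who can be in the pilot.** Let a girls have disclosed HIV only and b pregnancy only. The undisclosed counts are 30 − a for HIV and 30 − b for pregnancy. They sum to 60 − (a + b), which lies between 30 and 60. The document gives neither a nor b.

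**3. Possible dilution of the self-efficacy change.** Let p be the share already disclosed for a condition, and r their mean change relative to the undisclosed. Both are assumptions. Pooled change as a fraction of the undisclosed girls' change is (1 − p) + p·r = 1 − p(1 − r).

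| Already disclosed, of 30 | r = 0 | r = 0.5 | r = 1 | r = 1.25 |
|---|---|---|---|---|
| 3 | 0.90 | 0.95 | 1.00 | 1.025 |
| 6 | 0.80 | 0.90 | 1.00 | 1.05 |
| 10 | 0.67 | 0.83 | 1.00 | 1.08 |
| 15 | 0.50 | 0.75 | 1.00 | 1.125 |

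With 10 of 30 already disclosed, a change of 0.59 SD in the other 20 appears as 0.59 × 0.667 = 0.39 at r = 0, 0.59 × 0.833 = 0.49 at r = 0.5, and 0.59 at r = 1. The direction depends wholly on r. The r = 0 column requires that girls who have told one caregiver gain nothing, although they may still face telling other relatives. Nothing in the document favours r = 0 over r = 1.

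**4. Disclosure incidence.** If the event were a first disclosure to a caregiver, the rate over 30 girls could not exceed (number at risk)/30: 90% with 27 at risk, 80% with 24, 67% with 20 and 50% with 15. But the document does not define the event that way. Eligibility concerns a caregiver, whereas the measure listed in section 11 concerns family members in general. A girl who has told her mother can still tell an aunt. The ceiling holds only under a definition that the plan does not state.

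**5. What a split would cost.** The 95% half-width of a mean change in SD units is t(0.975, n−1)/√n: 0.37 at n = 30, 0.42 at 24, 0.47 at 20 and 0.55 at 15. The detectable dz rises from 0.589 at 30 to 0.739 at 20 and 0.876 at 15. The largest dilution in the table takes 0.59 to 0.295, a shift of 0.295 SD, which is inside the 0.37 half-width of the all-participant mean.

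**The case for a change.** The best case for a change is that it is cheap and would be fixed before results are seen. A few sentences could commit the team to tabulating the mix, to showing each self-efficacy change among girls with that condition undisclosed, and to defining the disclosure event and its denominator. Status has to be established at screening anyway, so no visit is added. Writing the split down beforehand would prevent choosing it because it looks better. And an incidence without a stated event and denominator is incomplete.

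Most of this stands as advice on reporting. A table of the baseline mix (neither disclosed, HIV only, pregnancy only) would help any reader, and the report must say what counts as a disclosure and among whom. None of it shows that a planned summary is wrong, though. The intervention is designed to help such girls "improve stigma knowledge and coping skills, HIV and pregnancy disclosure skills, and enlisting support of caregiving family members", and every pilot participant receives the session, so the mean over all of them answers a sensible question about the population the rule admits. The proposed additions would leave that mean and the .59 as they are. Nor is the point peculiar to self-efficacy: anticipated HIV stigma from family could also depend on whether family already know. That makes it a general feature of a mixed sample, not a defect in two outcomes. The incidence argument also weakens once it is read as the plan frames it: the secondary aim asks whether disclosure can be measured well, and leaves its use as a primary outcome to a later trial.

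**Conclusion.** No change to the plan follows. It is true that the pilot admits girls with one condition already disclosed, and that the plan neither splits results by that status nor gives a denominator for disclosure incidence. The all-participant summary is nevertheless valid. Any dilution ranges from none at r = 1 to half of the change when 15 of 30 have disclosed and gain nothing, and it reverses if they gain more. The document supports no value for either assumption, so neither the direction nor the size can be established. The cap on incidence depends on a definition that the plan does not contain.

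In an exploratory, descriptive pilot of 30 girls that already asks about disclosure at baseline, this is a gap that analysts can fill when they report: show the baseline mix, state the disclosure event, and choose the denominator to match. This rests on disclosure status being recorded separately for each condition, which the eligibility rule in effect requires.

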**Aim 1 adolescent participants:** N=24 adolescents will participate in an IDI and N=24 adolescents will participate in a dyadic interview with a family caregiver (**Component 1**), N=32 adolescents will participate in an FGD (4 FGDs comprised of 8 participants each, **Component 2**), and N=30 adolescents will participate in the pilot study (**Component 3**). Inclusion criteria: All adolescent participants will be female, currently pregnant, unmarried, 15-19 years old and have been diagnosed with HIV and aware of this diagnosis. They will collectively have a range of disclosure experiences (disclosed pregnancy and HIV status to a caregiving family member, disclosed one of the two conditions, has not disclosed either condition). Exclusion criteria: An adolescent will be excluded if she: (1) does not meet all inclusion criteria, (2) already participated in a study activity, or (3) does not show understanding of consent based on our consent assessment.

**Aim 1 caregiving family member participants (N = 24, Component 1):** They will be the family member who participates in the dyadic interview with an ALHIV. Inclusion criteria: Caregiving family member (e.g., parent, guardian, grandparent, sibling or other relative) of a pregnant unmarried ALHIV who is aged 15-19. They will be age 20 or older and may be female or male. Exclusion criteria: Caregivers will be excluded if they: (1) do not meet all inclusion criteria, (2) already participated in a study activity, or (3) are a romantic/sexual partner or a family member of a romantic/sexual partner of a pregnant ALHIV (rather than a member of her family).

**Aim 2 caregiving family member participants (N = 64, Component 4):** Inclusion criteria: Like the Aim 1 caregivers, they will be a caregiving family member of a pregnant unmarried ALHIV who is aged 15-19, aged 20 or older, and may be female or male. They may or may not be the family member of an Aim 1 participant. They will participate in one FGD session. Exclusion criteria: Caregivers will be excluded if they: (1) do not meet all inclusion criteria, (2) already participated in a study activity, or (3) are a romantic/sexual partner or a family member of a romantic/sexual partner of a pregnant ALHIV (rather than a member of her family).

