**Recruitment of caregivers (Components 1 and 4):** Caregiving family members will be a parent, guardian, grandparent, sibling, or other relative of a pregnant ALHIV who is responsible for the adolescent's care, food, and/or shelter. Study staff will ask adolescents who have disclosed their HIV status and pregnancy to family member(s) if there is a caregiver whom they recommend being invited to participate in the dyadic interview or focus groups. ALHIV will be informed that recommending a caregiver for a dyadic interview or focus group is optional and not required for study participation. ALHIV will give their permission for their caregivers to be recruited for the study (either for a dyadic interview or for the Aim 2 FGD). We expect that some pregnant ALHIV who have disclosed both conditions will decline to nominate a caregiver and for their safety we will not ask those who have not disclosed either or both conditions to nominate a caregiver. Only ALHIV who have disclosed their conditions and the caregiver to whom they have disclosed their conditions will be invited to participate in dyadic interviews.

As needed, in order to achieve our Aim 2 sample targets (**Component 4**), we will recruit additional family member caregivers of pregnant unmarried ALHIV aged 15-19 from the community and clinics. For

example, we will seek assistance from providers to recruit eligible caregivers in their catchment areas. We also will place posters with a brief study description and contact information for study staff in the health facilities and other public venues that interested caregivers of pregnant ALHIV may use to contact research staff. We will recruit only caregivers who already are aware they are caring for an adolescent who is both pregnant and living with HIV. We will conduct eight FGDs in Aim 2 (4 rural, 4 urban; 8 participants per FGD; n=64) in two rounds. In round 1, we will present Aim 1 findings, obtain caregivers' perceptions about whether the findings resonate with their experiences, and explore acceptable approaches to strengthen caregivers' skills. In round 2, we will present the final Aim 1 prototype and obtain caregivers' views, including about the acceptability of a complementary digital intervention for caregivers.

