**Risk of inadvertent disclosure of HIV and/or pregnancy status:** The young woman's HIV status or pregnancy could be inadvertently revealed to family or community members and result in her experiencing stigma. This could happen if someone who does not already know about the adolescent's pregnancy and/or HIV status were to learn that the adolescent or a caregiver is participating in a study for pregnant ALHIV and their caregivers. Accidental disclosure also could occur if a bystander were to overhear an interview or other data collection session in which HIV and/or pregnancy status is revealed. Although participants in the FGDs and pilot study interviews will not be asked personal questions, it is possible that some participants could reveal their HIV and pregnancy status when answering questions. A potential consequence of inadvertent HIV or pregnancy disclosure is violence from a partner, family member, or other person who is upset or who blames the young woman. In addition, adolescent or

caregiver participants could worry about such accidental disclosure occurring, which could result in them experiencing stress and anxiety.

**Risk of emotional distress during data collection sessions:** Some of the adolescent and caregiver participants in the interviews or pilot study could feel uncomfortable or emotionally distressed answering questions about themselves or their family member being pregnant; being HIV-infected; or experiencing problems regarding stigma, disclosure or social support. It also is possible that some participants may think about and disclose upsetting events (e.g., sexual abuse, intimate partner violence, or interpersonal conflict) during the data collection session. FGD participants will not be asked personal questions, but some individuals could potentially think about personal and sensitive thoughts during the research activity.

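### Girls with undisclosed HIV or pregnancy may be asked to pass on study flyers, although the plan withholds another optional request from the same girls for their safety

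*Combined protocol and SAP*

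**What the plan says.** Section 10(d), Sampling procedure, adds snowball sampling to clinic referral: "We will ask ALHIV and caregivers who participate in study activities if they are willing to assist with recruitment". The next sentence opens with its reason: "To ensure the privacy of potential participants, we will provide participants who are willing to assist with recruitment". The method is to supply these helpers "with up to two flyers each to pass on to potentially eligible ALHIV and caregivers in their communities". On content it says only this: "The flyer will include instructions for individuals who are interested in participating in the study".

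The same section sets disclosure status by component. For the pilot, "Pilot study participants will not have disclosed at least one of the two conditions to a caregiver". The in-depth interviews and focus groups are to include both girls who have disclosed and girls who have not. The dyadic interviews take only girls who have disclosed both conditions. Section 10(c) gives the pilot size: "N=30 adolescents will participate in the pilot study".

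Under Recruitment of caregivers, section 10(d) makes nominating a caregiver optional and then adds a restriction: "for their safety we will not ask those who have not disclosed either or both conditions to nominate a caregiver".

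Section 12(a), on the risk of inadvertent disclosure, describes the case in which a person unaware of a girl's pregnancy or HIV status "were to learn that the adolescent or a caregiver is participating in a study for pregnant ALHIV and their caregivers". It names violence as a possible consequence.

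**The concern.** The snowball rule covers ALHIV participants without regard to component or disclosure status. A girl whose family does not know she is pregnant or living with HIV can therefore be asked to take study flyers away with her and hand them to others, caregivers included. If the flyer describes the study population, having it or giving it to someone can tie her to a study of pregnant girls living with HIV. Section 12(a) identifies learning of participation as a way in which status becomes known.

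The plan sees a related hazard when it comes to nominating caregivers and protects non-disclosed girls there. The flyer rule carries no matching protection, and its stated privacy purpose looks only to the people being recruited. What is at stake is an avoidable route to a harm that the plan itself names, among girls for whom it has otherwise taken particular care.

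**Working it through.** No power or error-rate figure bears on this point. The check is a count of who falls under the rule, followed by a comparison of the relevant passages.

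**Who falls under the rule (section 10(c) sizes, section 10(d) disclosure criteria)**

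- Adolescents in all: 24 in-depth interview + 24 dyadic + 32 focus group + 30 pilot = 110. This reproduces the figure in the Lay Summary.
- Dyadic interviews: all 24 have disclosed both conditions.
- Pilot: all 30 have at least one undisclosed condition, by eligibility.
- In-depth interviews and focus groups: 24 + 32 = 56, deliberately mixed. The non-disclosed number is more than 0 and fewer than 56; the documents give no split.
- Non-disclosed girls within reach of the request: more than 30 and fewer than 30 + 56 = 86.
- Flyers that pilot girls could hold: at most 30 × 2 = 60. This ceiling is reached only if every girl agrees and takes two.

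**How the plan treats these girls in each place**

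1. *Nominating a caregiver* (section 10(d), Recruitment of caregivers). The act is optional, yet girls with either or both conditions undisclosed are not asked, and safety is the reason given.
2. *Passing on flyers* (section 10(d), Sampling procedure). The act is also optional. There is no exclusion by disclosure status, and the privacy reason concerns potential participants.
3. *Telling parents about the study* (section 12(a), waiver of parental consent). This happens only with the girl's permission, and staff must keep the description general enough to give away nothing she has not disclosed.
4. *Flyer wording* (section 10(d), Sampling procedure). Instructions for interested people are promised. No commitment to general or neutral wording is made.
5. *Safeguards against inadvertent disclosure* (section 12(a)). These cover private venues, individual sessions, staff sensitivity to disclosure circumstances, care when entering homes, restriction of dyadic caregivers to those who know both conditions, and data security. Neither flyers nor the participant who carries them are mentioned.

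Items 1 and 3 show the standard the plan sets for girls with something undisclosed. Items 2 and 4 do not apply it, and item 5 does not make up the difference.

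**The case against.** The strongest reply has four parts.

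- *Helping is voluntary.* This is correct: girls are asked whether they are willing, and only the willing receive flyers. But nomination is optional too, and the plan still chooses not to ask. On its own reasoning, being free to decline is not protection enough.
- *The two rules govern different acts.* This stands. A nomination leads staff to invite a family member, whereas a girl with flyers decides who gets one, if anyone. A reader might infer that the plan contradicts itself; it does not. The same group is protected in one place and left unaddressed in another.
- *The flyer may already be neutral.* It may be, and its absence from the documents is no evidence that it is unsafe. The Data and Safety Monitoring Plan is a separate attachment, and two ethics boards review the study. The size of the risk is therefore unknown. What can be said is that the text makes no commitment on wording.
- *Staff are trained to be alert to accidental disclosure.* This helps, but it is not a rule about who is offered flyers.

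A reader might also infer that the pilot results are threatened, either because a disclosure caused by a flyer would be counted as an outcome, or because recruits would hear about the app before their baseline survey. The documents do not support that as a finding. Nothing suggests that flyers would be a material source of disclosures, and disclosure is a secondary outcome examined to see whether it can be measured well. The prototype is used one-on-one on a study phone, girls at the same clinic could talk without any flyer, and the pilot is a descriptive single-group study with no comparison arm.

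**Conclusion.** The point holds as a gap in protection. The flyer rule reaches all 30 pilot girls and an unstated share of the 56 interview and focus-group girls, all with at least one condition undisclosed to a caregiver, and gives them none of the protection they receive over caregiver nomination. It rests on reading the snowball sentence as it is written: it does not say that every girl must be asked, but it makes no exception.

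The counts show whom the rule can reach, not how many would be harmed. Uptake is voluntary, the split within the 56 is not given, and the hazard depends on flyer text that cannot be seen. Nor do the documents make inadvertent disclosure the leading harm: the risk paragraphs set it beside emotional distress without ranking the two. The change is still worth making before recruitment starts, because it is small and follows a standard the plan already applies.

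**What to change.** In section 10(d), Sampling procedure, make two changes:

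1. Offer flyers only to caregivers and to ALHIV who had disclosed both conditions to a caregiver when screened. This mirrors the restriction on nomination and excludes pilot participants by definition. Screening already has to establish disclosure experience, so no new data are needed.
2. Commit to flyer wording that names neither HIV nor pregnancy, in keeping with the general description section 12(a) requires when parents are told about the study. This also protects those who still carry flyers, since disclosure to one caregiver does not mean that others know.

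A line under the section 12(a) safeguards should record both, so that the passages agree.

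The cost is somewhat slower snowball recruitment of non-disclosed girls, the group the pilot needs. Referral by clinic providers and posters continue as planned. Neutral wording may bring some enquiries from ineligible people, which the existing screening step can handle.
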